To minimize the risk of severe adverse event in frail subjects enrollment of Elderlies-cohort will start after that 4-week safety results in Adults-Cohort will be available. Moreover, as it is a first in human trial, we have scheduled volunteers to be enrolled according to a strict frame of authorization rules. In particular, each arm includes two groups (A and B). Group As are made of 3 volunteers each to be enrolled throughout a week. The occurrence of SAE within 48h since the injection will be reported to data safety monitoring board (DSMB) and the enrolment suspended until a direct effect of the vaccination is excluded. Group Bs are made of 12 participant each to be enrolled over a week. DSMB provide binding advice on sequential enrollment across groups and arms; this is:

- enrolment of Arm-1 group B and Arm-2 group A is bound to a positive decision on 7-day safety of Arm-1 group A;
- enrolment of Arm-2 group B and Arm-3 group-A is bound to a positive decision on 7-day safety of Arm-2 group A;
- enrolment of Arm-3 group B is bound to a positive decision on 7-day safety of Arm-3 group A;
- enrolment of Arm-4 group A is bound to a positive decision on 4-week safety Arm-1;
- enrolment of Arm-4 group B and Arm-5 group A is bound to a positive decision on 7-day safety of Arm-4 group A;
- enrolment of Arm-5 group B and Arm-6 group-A is bound to a positive decision on 7-day safety of Arm-5 group A;
- enrolment of Arm-6 group B is bound to a positive decision on 7-day safety of Arm-5 group A.

Figure 8 reports the flow-charts for authorization and enrollment.

[figure not shown]

Figure 8 Study design and enrollment flow charts according to DSMB binding decisions

6. Recruitment and withdrawal

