Physical examination	x	x	x	x	x	x	x	x	x	Medical visit
TC	x	x	x	x	x	x	x	x	x	
SpO2 %	x	x	x	x	x	x	x	x	x	
Pulse	x	x	x	x	x	x	x	x	x	
Blood pressure	x	x	x	x	x	x	x	x	x	
Urine analysis	x									
Urine B-HCG	x	x								Urine
Blood counts	x	x	x	x	x	x	x	x	x	
Biochemistry	x	x	x	x	x	x	x	x	x	
Coagulation	x									
HIV-Ab	x									
HBsAg and HCV	x									
HLA Typing				x						Blood test
SARS-CoV-2 Serology *	x									
CLIA anti-S (IgG)		x		x	x	x	x	x	x	
CLIA anti-N (IgG)		x		x	x	x	x	x	x	
Micro neutralization					x				x	
Elispot SARS-CoV-2		x			x	x	x	x	x	
Total blood volume (mL)	36	60	10	27	60	60	60	60	60	433

Figure 9 Timing of participant follow-up after vaccination. Scr=screening to be done no more than 21 days before vaccination; T0=day of the vaccination; D2= day 2 after vaccination; W1= one week after vaccination; W2= two weeks after vaccination W4= four weeks after vaccination; W8= eight weeks after vaccination; W12= twelve weeks after vaccination; W24= twenty-four weeks after vaccination. A) Diary given to participants; B) Diary received from participants.

* This is any serological assay to detect anti-SARS-CoV-2 total IgG which is validated for clinical use in Italy (i.e. validated for diagnosis of SARS-CoV-2 infection)

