9.5. Reporting procedure for all AE

All local and systemic AEs occurring in the 28 days following each vaccination observed by the Investigator or reported by the participants, whether or not attributed to study medication, will be recorded. Recording and reporting of all AEs will be detailed in SOP. All AEs that result in a participant withdrawal from the study will be followed up until a satisfactory resolution occurs or until a non-study related causality is assigned (if the participant consents to this). SAEs will be collected throughout the entire trial period (i.e. until W24).

SAEs will be reported on the SAE forms by doctors who enrolled participants to the principal investigator and DSMB. SAE will be documented accurately and notified within 48 hours to the DSMB. The DSMB will also review severity and causality analysis within 2 days and will provide advice on study continuation. AEs will be reported to DSMB within 7 days. In special circumstance the chair of DSMB may decide to involve the ethical committee to analyze AE reports in order to define how to continue the study.

SAR and SUSAR that occur within week 10 of the study will determine a temporal suspension of the enrollment pending the decision of DSMB. The suspension is decided by the local investigator and immediately communicated to principal investigator and DSMB. When a SAR or a SUSAR occurs among participants enrolled in a clinical center the investigator of the clinical center will immediately contact the principal investigator who will eventually contact other enrolling centers.

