9.8. Halting rules and study termination due to safety issue

Safety halting rules have been developed considering the fact that this is a *first-in-human* dose escalation study. Solicited adverse events are those listed as in section 9.2, occurring within the first 7 days after vaccination (day of vaccination and six subsequent days). Unsolicited adverse events are AE other than the solicited AEs occurring within the first 7 days, or any AEs occurring after the first 7 days after vaccination.

Enrolment of participants in one arm will be upheld if:

- A. Solicited local adverse events (site of injection): 2 or more vaccinations in a group are followed by the same severe solicited local adverse event beginning within 2 days after vaccination (day of

vaccination and one subsequent day) and persisting at severe for >48 hrs and these are deemed possibly, probably or definitely related to study interventions.

- B. Solicited systemic adverse events: If 2 or more vaccinations in a group are followed by the same severe solicited systemic adverse event beginning within 2 days after vaccination (day of vaccination and one subsequent day) and these are deemed possibly, probably or definitely related to study interventions.
- C. Unsolicited adverse events: If 2 or more vaccinations in a group are followed by the same serious unsolicited adverse event (including the same laboratory adverse event) and relation with vaccination cannot be immediately excluded.
- D. One participant with serious adverse event considered possibly, probably or definitely related to vaccination occurs
- E. Life-threatening condition when relation with study intervention cannot be immediately excluded.
- F. Death when relation with study intervention cannot be immediately excluded.

If a halting rule has been met, we will inform the regulatory authority. Moreover, before restarting enrollment the DSMB should exclude that AE has no immediate causal relation with the vaccine or that benefit of vaccination outweigh risk of further AE occurrence. In these latter case Ethical committee should be involved in the decision. Halting rules apply to one dose and the next higher one, so that if halting rule is met for the highest dose, only this arm is upheld. If halting is met for intermediate dose, two arms are held. If halting rule is met for the lowest dose all the study is stopped pending on the investigation of causal association between AE and vaccination (DSMB advice).

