#### [1] AE and Categorical Safety only

[Table 3](#) at Section 4.2.

Subject are provided with diary cards as indicated in Schedule of Assessments (Appendix 6.1) and instructed to record systemic and injection site adverse event in diary for four weeks post vaccination. Daily source data are entered in the respective Diary eCRFs.

Summary on severity will be provided over all systemic adverse events (Nausea, Vomiting, Diarrhea, Abdominal Pain, Headache, Muscular Pain, Fatigue and Chills), injection site pain and ulcer by treatment groups, days and weeks. By time point severity over all systemic adverse events will be calculated by counting the number of subjects in each severity categories in any AE term.

By-subject listings of diary data will include records with any severity as well as swelling, redness, ulceration and body temperature daily assessments.

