## 6 APPENDICES

### 6.1 Schedule of Assessments

**Table 5 Schedule of Assessments**

	Time of the visit since vaccination									
	Screening	T0	D2	W1	W2	W4	W8	W12	W24	
Window (days)	≤ 28	0	0	±1	±1	±2	±4	±7	±14	
Informed consent	X									
Eligibility	X									
Vaccination		X								
AE reporting	X	X	X	X	X	X	X	X	X	
Diary card		A		B	B	B§				
Checking diary card completeness			X	X	X	X				
Medical history										
Adverse Events	X	X	X	X	X	X	X	X	X	
Concomitant Medications	X	X	X	X	X	X	X	X	X	
Physical examination	X	X	X	X	X	X	X	X	X	
Body Temperature	X	X	X	X	X	X	X	X	X	
SpO2 %	X	X	X	X	X	X	X	X	X	
Pulse	X	X	X	X	X	X	X	X	X	
Blood pressure	X	X	X	X	X	X	X	X	X	
ECG	X									
Urine analysis	X									
Urine B-HCG	X	X								
Blood counts	X	X	X	X	X	X	X	X	X	
Biochemistry	X	X	X	X	X	X	X	X	X	
Coagulation	X									
HIV-Ab	X									
HBsAg and HCV	X									
HLA Typing				X						
SARS-CoV-2 Serology*	X									
CLIA anti-S (IgG)		X		X	X	X	X	X	X	
CLIA anti-N (IgG)		X		X	X	X	X	X	X	

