# Parexel International

ReiThera SRL.

RT-CoV-2

Statistical Analysis Plan

	Time of the visit since vaccination									
	Screening	T0	D2	W1	W2	W4	W8	W12	W24	
Micro neutralization						X			X	
ELISpot SARS-CoV-2		X			X	X	X	X	X	

Scr=screening to be done no more than 21 days before vaccination; T0= day of the vaccination; D2= day 2 after vaccination; W1= one week after vaccination; W2= two weeks after vaccination W4= four weeks after vaccination; W8= eight weeks after vaccination; W12= twelve weeks after vaccination; W24= twenty-four weeks after vaccination. A) Diary given to volunteers; B) Diary received from volunteers. §At week 4, diary cards for W3 and W4 will be collected.

\* This is any serological assay to detect anti-SARS-CoV-2 total IgG which is validated for clinical use in Italy (i.e. validated for diagnosis of SARS-CoV-2 infection). †no CRP testing at screening.

TP-GDO-WW-133-02

CONFIDENTIAL

Project Document Version No. 4.0

Effective Date: 26 Nov 19

Project Document Effective Date: 23-Jun-2021

Related to: SOP-GDO-WW-019

Page 33 of 33

Signature Page for VV-TMF-289681 v4.0

Reason for signing: Approved	Name: [name] Role: Biostatistics Date of signature: 23-Jun-2021 15:32:54 GMT+0000
------------------------------	---

Reason for signing: Approved	Name: [name] Role: Sponsor Date of signature: 24-Jun-2021 09:25:42 GMT+0000
------------------------------	---

Reason for signing: Approved	Name: [name] Role: Sponsor Date of signature: 28-Jun-2021 08:32:34 GMT+0000
------------------------------	--

Signature Page for VV-TMF-289681 v4.0

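### Protocol Figure 9 returns the diary card only at week 4, whereas SAP Table 5 also returns it at weeks 1 and 2; under the protocol schedule a group A's own diary comes back about three weeks after the 7-day data point on which its DSMB gate rests

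*Protocol*

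**What the plan says.** **Diary return.** In protocol Figure 9 (section 7.3) the diary row has A at T0 and B at W4, with D2, W1 and W2 blank. The legend reads "A) Diary given to participants; B) Diary received from participants". The protocol mentions the diary nowhere else.

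SAP Table 5 (section 6.1) has A at T0 and B at W1, W2 and W4. Its footnote says "At week 4, diary cards for W3 and W4 will be collected", so return in weekly parts is intended. It also has a row, "Checking diary card completeness", marked at D2, W1, W2 and W4, which Figure 9 lacks. SAP 4.12.1 says that participants are "instructed to record systemic and injection site adverse event in diary for four weeks post vaccination" and that the daily entries go into diary eCRFs.

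**Gates.** Protocol section 5 makes enrolment depend on DSMB decisions, beginning with "enrolment of Arm-1 group B and Arm-2 group A is bound to a positive decision on 7-day safety of Arm-1 group A". Six of these decisions concern 7-day safety of a group A. The seventh, which opens Arm-4, concerns 4-week safety of Arm-1.

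**Rules that use the data.** Halting rule A (section 9.8) concerns a severe solicited local reaction that starts on the day of vaccination or the day after, "persisting at severe for >48 hrs and these are deemed possibly, probably or definitely related to study interventions". On reporting, section 9.5 says "AEs will be reported to DSMB within 7 days"; SAEs have a 48-hour limit.

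**The concern.** The two schedules disagree on when the daily reactogenicity record reaches the site. The difference falls across the point at which the protocol uses 7-day safety to release the remaining 12 participants of an arm and, at four of the six gates, the first three at the next dose.

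The diary holds day-by-day severity for injection-site pain and systemic symptoms, and daily swelling, redness and temperature (SAP 4.12.1). If Figure 9 is followed, a gate on 7-day safety is taken while the gating group's cards are still with the participants. The onset and duration of reactions between visits then rest on history or telephone reports, without the daily record to confirm them. Separately, the AE reporting limit is as long as the observation window itself, so timely reporting does not ensure that an event is before the DSMB at the gate.

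**Working it through.** **1. Gate count.** Section 5 lists seven decisions: six on 7-day safety and one on 4-week safety. SAP 4.11.7 plans seven DSMB meetings, so the plan's own figure is reproduced.

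**2. Lag of a group's own diary.** Figure 9 windows: W1 = 7±1, so day 6 to 8; W4 = 28±2, so day 26 to 30.

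- Nominal: 28 − 7 = 21 days
- Shortest: 26 − 8 = 18 days
- Longest: 30 − 6 = 24 days

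Under SAP Table 5 the first return is W1 itself, so the lag is nil.

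**3. Gate day against diary day.** The documents fix no vaccination days within a group A beyond the 48-hour spacing, so three paces are assumed. On the nominal two-week cycle (group A vaccinated over one week on days 0, 2 and 7, then 7 days of follow-up) the gate falls on day 14 from the group's start. On days 0/2/4 with no DSMB delay it falls on day 11, and on days 0/2/2 on day 9. The earliest possible W4 return in the group is day 26, so the group's own diary misses its gate by at least 26 − 14 = 12 days at every pace.

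**4. Gates that rest on a preceding group.** As written in section 5, Arm-6 group B depends on Arm-5 group A, not Arm-6 group A. That gate falls two cycles after Arm-5 group A starts:

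| Pace | Gate day | Arm-5 group A diaries due | In hand |
|---|---|---|---|
| Nominal cycle | 28 | 28, 30, 35 | 1 of 3 |
| 0/2/4 | 22 | 28, 30, 32 | 0 of 3 |
| 0/2/2 | 18 | 28, 30, 30 | 0 of 3 |

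This gate is therefore borderline. Section 7.7 also names different gating groups from section 5: Arm-2 group A for Arm-3 group B, and Arm-4 group A for Arm-5 group B with Arm-6 group A. Those passages must be reconciled too.

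**5. Diaries from earlier participants.** Arm-1 group A diaries in hand at the three adult 7-day gates, at nominal visit days:

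| Pace | Gate days | Diaries due | In hand |
|---|---|---|---|
| Nominal cycle | 14, 28, 42 | 28, 30, 35 | 0, 1, 3 |
| 0/2/4 | 11, 22, 33 | 28, 30, 32 | 0, 0, 3 |
| 0/2/2 | 9, 18, 27 | 28, 30, 30 | 0, 0, 0 |

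The elderly gates all follow the Arm-1 4-week decision, which needs full data on at least 12 of 15 participants (section 7.7). Arm-1 diaries are therefore due before all three elderly 7-day gates.

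**6. Halting rule A.** The D2 visit is at 48 hours. A reaction that starts immediately after vaccination has not yet exceeded 48 hours then. With onset on day 0 or 1, the threshold is passed on about day 2 or 3 (0 + 2, 1 + 2), after D2 and before W1 on day 6 to 8. The persistence criterion is thus always completed between visits. Rule B has no persistence test, so this step does not apply to it.

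**7. Reporting limit.** The solicited window is the day of vaccination plus six days. An event on the last day, counted from its onset, may be reported up to day v + 6 + 7 = v + 13, where v is the vaccination day:

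| Pace | Limit for the three members | Gate day |
|---|---|---|
| 0/2/7 | 13, 15, 20 | 14 |
| 0/2/4 | 13, 15, 17 | 11 |
| 0/2/2 | 13, 15, 15 | 9 |

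A non-serious event can be reported within the limit and after the gate for two or all three members.

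**The case against.** The strongest reply is that the gates do not depend on the diary. For the 7-day review, section 7.7 names a medical visit and laboratory tests. AEs are assessed at D2 and W1 (section 7.8), participants have a contact number (section 7), and events they report are evaluated by telephone at once (section 9.6). AE listings carry onset date, resolution date, duration and severity (SAP 4.11.1). A reader might infer that the gates are decided on recall alone, or that the halting rules cannot be evaluated; the documents support neither. What remains is that, for an event between D2 and W1, those dates would be entered without the daily record.

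A second reply is that a severe reaction under section 9.2 involves invasive intervention or hospitalization, and hospitalization is an SAE notified within 48 hours. This stands for such events. It does not cover every severe local reaction, because Table 1 (section 9.7) grades erythema and swelling by size alone.

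A third is that the documents may come from different protocol versions. The SAP rests on Version 2.0, cites section 8.3 for what is section 7.3 here, and its schedule differs elsewhere (a 28-day against a 21-day screening window, and an added ECG row). The diary row may already have been amended. The documents do not settle this, so the fix begins there.

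The DSMB charter and the AE reporting SOP, which may specify the data cut, were not available.

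**Conclusion.** The contradiction between Figure 9 and SAP Table 5 holds. Under Figure 9 the gating group's own diary is due 18 to 24 days after the 7-day data point. This applies to six of the seven gates, with Arm-6 group B borderline as written. The loss is of contemporaneous daily severity data, most relevant to halting rule A; it is not an absence of safety data.

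A reader might go further and say that all six gates are decided before any diary in the trial is in hand. That is true of only one to three of the six, depending on pace. The six gates release 15 + 15 + 12 + 15 + 15 + 12 = 84 of 90 participants, but this counts everyone released through them, not people exposed because of the diary row.

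The conclusion assumes that gates are decided soon after the 7-day data, as section 7.7 indicates, and that the columns of Figure 9 are read correctly. The second deserves a check against the PDF: the micro-neutralization row there reads W2 and W24, against weeks 4 and 24 in protocol 4.2.2 and SAP Table 5. If the diary mark belonged one column earlier, at W2, the nominal lag would shrink to 14 − 7 = 7 days but would not vanish.

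**What to change.** - Confirm which protocol version governs, and reconcile Figure 9 with SAP Table 5 so that the week-1 diary card is collected and checked at the existing W1 visit.
- Reconcile sections 5, 7.7 and 9.5 so that the safety data cut sent to the DSMB for a 7-day gate covers that group's week-1 diary and all AEs with onset in the window. This defines the data supplied; it does not alter the escalation or halting criteria.
- In the same amendment, reconcile the gating groups named in sections 5 and 7.7.

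The cost is an amended schedule and a few sentences. No visit is added. The downside is that a gate may wait briefly for three diary cards.

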7.4. Immunogenicity analysis

Tests for assessing immunogenicity will be carried out at INMI Lazzaro Spallanzani laboratory at the endpoints indicated in the schedule of procedures. Management of samples and methodology of testing are reported in section 6. Testing for immunogenicity includes:

- A. CLIA to quantify antibodies to SARS-CoV-2 S-protein (anti-S-Ab)
- B. CLIA to quantify antibodies to SARS-CoV-2 N-protein(anti-N-Ab)
- C. SARS-CoV-2 micro-neutralization assay to quantify neutralizing antibody activity to the virus
- D. Ex vivo IFN-gamma ELISpot responses to SARS-CoV-2 S-protein

Other exploratory immunological assays including analysis polyfunctional T cell analysis and other antibody assays will be performed at the discretion of the investigators.

7.5. Screening

A month before starting the enrolment a set of subjects will undergo medical screening including a medical visit (pulse, blood pressure, temperature, medical history, physical examination, ECG) blood testing and urine analysis. Testing for screening is reported in Figure 9. Biochemical test valid for enrollment should be carry out no more than 21 days before vaccination.

7.6. Enrolment visit (Time 0)

Before vaccination, the eligibility of each participant will be reviewed. Investigator will check pulse, blood pressure, temperature, medical history, physical examination and carry out a blood sampling. Testing for time 0 is reported figure 9.

7.7. Vaccination sequence

For safety reasons enrolment of *first in human* vaccine administration will be carried out on a weekly sequence in the six different arms. Each arm will be divided into 2 groups. Group-A are made of 3 volunteers each and group-Bs are made of 12 volunteers each.

At the beginning of the study clinical center will smoothly screen eligible subjects.

At enrollment on day 1 the first participant (arm 1 group-A) will be vaccinated ahead of any other participants and the profile of adverse events will be reviewed 48 hours after vaccination. Provided there are no safety concerns, as assessed by the local medical investigators, another two participants will be vaccinated at the same dose after at least 48 hours has elapsed following the first participant. Thus within one week, three participants will be vaccinated.

The following week the three participants vaccinated will undergo clinical screening for AE including a medical visit and a laboratory tests up to 7 days after vaccination. DSMB will analyze data on safety for arm 1 group-A and provide binding advice for the eventual enrolment. Eventual enrollment will include two blocks of participants this is:

- A. Arm 1 group-B (12 participants)
- B. Arm 2 group-A (3 participants)

Participants in arm 2 group-A will be scheduled for vaccination similarly to those vaccinated in arm 1 group-A, 48 hours apart from each other, provided there are no safety concerns, as assessed by the local medical investigators. Participants in arm 1 group-B will be smoothly vaccinated throughout the week.

The participants vaccinated in arm 2 group-A and arm-1 group-B undergo clinical screening for AE including a medical visit and a laboratory tests up to 7 days after vaccination. DSMB will analyze data on safety for arm 2 group-A and provide binding advice for the eventual enrolment. Eventual enrollment will include two blocks of participants this is:

- A. Arm 2 group-B (12 participants)
- B. Arm 3 group-A (3 participants)

Participants in arm 3 group-As will be scheduled for vaccination similarly to those vaccinated other group-As, 48 hours apart from each other, provided there are no safety concerns, as assessed by the local medical investigators. Participants in arm 2 group-B will be smoothly vaccinated throughout a week.

The participants vaccinated in arm 3 group-A and arm 2 group-B will undergo clinical screening for AE including a medical visit and a laboratory tests up to 7 days after vaccination. DSMB will analyze data on safety for arm 2 group-A and provide binding advice for the eventual enrolment. Eventual enrollment will include one block of participants this is:

- A. Arm 3 group-B (12 participants)

Participants in arm 3 group-B will be smoothly vaccinated throughout the week.

The participants vaccinated in arm 3 group-b will undergo clinical screening for AE including a medical visit and a laboratory tests up to 7 days after vaccination. DSMB will analyze data and provide a general advice on vaccine safety at the conclusion of enrollment of the Adult-Cohort.

When data on 4-week safety for the whole arm 1 (15 participants) will be available. DSMB will provide binding advice for the eventual enrolment in the Elderlies-Cohort. The decision will be done only if no less than full data of 12 out of 15 participants will be available.

The enrollment the Elderlies-Cohort will follow the same scheme of the enrollment of Adults-Cohort.

The first participant of the Elderly-Cohort (arm 4 group-A) will be vaccinated ahead of all other elderlies participants. Provided there are no safety concerns, as assessed by the local medical investigators, another two participants will be vaccinated at the same dose after at least 48 hours has elapsed following the first participant. By the end of a week, three participants will be vaccinated.

All the participants vaccinated in ARM 4 group-A will undergo clinical screening for AE including a medical visit and a laboratory tests up to 7 days after vaccination. DSMB will analyze data on safety for arm 4 group-A and provide binding advice for the eventual enrolment. Eventual enrollment will include two blocks of participants this is:

- A. Arm 4 group-B (12 participants)
- B. Arm 5 group-A (3 participants)

Participants in arm 5 group-A will be scheduled for vaccination similarly to those vaccinated group-As, 48 hours apart from each other, provided there are no safety concerns, as assessed by the local medical investigators. Participants in arm 4 group B will be smoothly vaccinated throughout the week.

The participants vaccinated in arm 5 group-A and those vaccinated in arm 4 group-B will undergo clinical screening for AE including a medical visit and a laboratory tests up to 7 days after vaccination. DSMB will

analyze data on safety for arm 4 group-A and provide binding advice for the eventual enrolment. Eventual enrollment will include two block of participants this is:

- A. Arm 5 group-B (12 participants)
- B. Arm 6 group-A (3 participants)

Participants in arm 6 group-A will be scheduled for vaccination similarly to those vaccinated group-As, 48 hours apart from each other, provided there are no safety concerns, as assessed by the local medical investigators. Participants in arm 5 group B will be smoothly vaccinated throughout the week.

The participants vaccinated in arm 5 group-A and those vaccinated in arm 5 group-B will undergo clinical screening for AE including a medical visit and a laboratory tests up to 7 days after vaccination. DSBM will analyze data on safety for arm 5 group-A and provide binding advice for the eventual enrolment. Eventual enrollment will include one block of participants this is:

- A. Arm 6 group-B (12 participants)

Participants in arm 3 group-B will be smoothly vaccinated throughout the week.

The participants vaccinated in arm 6 group-B clinical screening for AE including a medical visit and a laboratory tests up to 7 days after vaccination. No more participants will be vaccinated.

